# C) RESEARCH DESIGN AND METHODS

#### **Trial Design Summary**

The proposed proof-of-concept study will use an 18-month randomized, placebo-controlled, double-blind, parallel-group clinical trial design to investigate the effects of IPE (available as Vascepa® in the United States) on rCBF, CSF AD biomarkers, and cognition in 150 cognitively-healthy Veterans ages 50-75 years at increased risk for AD due to their Veteran-related risk factors including high vascular risk profiles, TBI, and PTSD. The primary aim of the trial (**Specific Aim 1**) is to assess whether IPE increases 18-month rCBF in a statistically-defined region of interest (sROI) in a population of middle-aged veterans compared to placebo. Key secondary aims within this proof-of-concept pilot RCT are: (**Specific Aim 2**) to assess whether IPE decreases CSF A $\beta$ 42; and (**Specific Aim 3**) to assess whether IPE improves cognitive performance on the ADCS-PACC battery compared to placebo. Data collected within this clinical trial will also allow exploratory analyses of the effects of IPE on measures of axonal and neuronal health, including CSF biomarkers (total tau, phosphorylated tau [p-tau], neurofilament light [NFL] protein, soluble amyloid precursor protein  $\alpha$  and  $\beta$  [sAPP- $\alpha$  and sAPP- $\beta$ ], monocyte chemotactic protein 1 [MCP1], YKL-40, and other CSF measures) and neuroimaging biomarkers (diffusion

weighted imaging, volumetric changes, 4D flow measures, and white matter hyperintensity measures among others). In addition, data collection from this trial will allow for exploration of the impact of previous TBI and/or PTSD on response to therapy. We hypothesize that in this population, IPE will beneficially affect mechanisms central to AD pathology by: 1) increasing rCBF within the sROI; 2) reducing CSF A $\beta$ 42; and that these neurobiological changes will be associated with 3) an increased ADCS-PACC cognitive composite score. While recognizing that the proposed trial is not addressing all potential effects of IPE, such as changes in measures of inflammation or oxidative stress, we will store neuroimages and blood and CSF samples for future analyses of other potential mechanisms.

Table 2. Study Design

VA BRAVE-EPA STUDY	Visit Number/Month (+/- 8 weeks)								
VA DRAVE-LPA STODI	Pre-	Bse	V2	V3	V4	V5	V6	V7	Final (Or
	Study	V1	M1	M3*	M6*	M9	M12*	M15*	Early
	V0	M0							Termination)
	M-1								Visit V8 M18
Eligibility review	Х								
Informed consent	Х								
Past medical history & medication review	Х	Х	Х	Х	Х	Х	Х	Х	Х
Side effect review			Х	Х	Х	Х	Х	Х	Х
Randomization		Х							
Medication dispensing		Х	Х	Х	Х	Х	Х	Х	Х
Pill count			Х	Х	Х	Х	Х	Х	Х
Participant honorarium given		Х				Х			Х
Screening cognitive tests									
MoCA, CERAD List Learning	Х								
Dietary Food Frequency Questionnaire		Х				Х			Х
Screening questions									
Deployment history, TBI, PTSD		Х							
Hamilton Depression Rating Scale		Х	Х	Х		Х			Х
MINI International Neuropsychiatric		Х							
Interview (subset)									
Vitals, anthropometrics	X	X	X	Х		Х			X
Physical and neurologic exam		X				Х			X
ADCS-PACC cognitive test battery		X				Х			X
Lumbar puncture		X				Х			Х
MRI (ASL, VIPR, FLAIR, DWI)		X				Х			Х
Screening/safety labs									
Fasting lipid profile (TC, TG, HDL, LDL)	X	X				Х			Х
glucose	Х	Х				Х			Х
High sensitivity c-reactive protein		Х				Х			Х
AST, ALT	Х	Х	Х	(X)**	(X)**	X	(X)**	(X)**	Х
creatinine	Х	Х				Х			Х
Urine pregnancy (if of childbearing	Х	Х	Х	Х	Х	Х	Х	Х	Х
potential)									
Complete blood count	Х								
CSF cell count with differential		Х				Х			Х
APOE genotyping***	Х								

CSF Aβ42, tau, p-tau-181, Aβ40, NFL	(		Х		X
([name] lab)					

\*Month 3, 6, 12, and 15 visits may be done remotely over the phone with labs drawn and a pregnancy test completed locally if participant travels from a distance or as required/requested during COVID. Medications will be shipped to participants and any remaining pills returned at their next in-person visit for pill counts.

\*\*Participants with baseline or month 1 AST or ALT between 1.5 upper limit of normal (ULN) and ≤2 x ULN at the preceding visit will have repeat AST and ALT values drawn at 3-, 6-, 12- and 15-month visits as well.

\*\*\*After final visit, whole blood collected at the Pre-Study visit will be used for APOE genotyping.

To test this hypothesis, we will enroll 150 cognitively healthy male and female Veterans and randomize them in a 1:1 ratio to IPE 4 g daily or matching placebo. All participants will undergo informed consent and will be screened for eligibility via a pre-study screening visit (Table 2). At baseline and months 9 and 18, all participants will undergo MRI, lumbar puncture (LP) for CSF collection, a blood draw, cognitive testing, vascular risk assessment, and will complete questionnaires including a food frequency questionnaire (FFQ) targeting omega-3 fatty acid intake and screening questions assessing prior combat and non-combat deployment, TBI, PTSD, and related sequelae. At months 1, 3, 6, 12, and 15, participants will have an assessment of medical/medication changes and potential side effects, interim lab assessments as indicated (aspartate transaminase [AST], alanine transaminase [ALT], urine pregnancy as needed) (Table 2), have vitals and body measurements collected, and be evaluated for depression using the Hamilton Rating Scale for Depression (HAM-D) test. As detailed in the Statistical Analysis section, using a two-sided test at the 0.05 level and anticipating a conservative 90% retention rate, a sample size of 150 participants will provide 90% power to detect significant changes in our primary and key secondary outcomes. Specifics of the above procedures are outlined below.

We will aim to schedule study visits within 8 weeks of the target visit time, but it is possible that the actual visit will be outside of this window. If the final visit is delayed, we may ask the participant to remain on the study medication for no more than 6 additional months based on statistical analysis, resources, funding, or other factors. This will ensure the study team to collect accurate results at the participant's final biomarker visit.

If the participant does not bring their remaining study medication to their final visit, we will provide them with a postage-paid envelope to return the medication to the study team for disposal. If this envelope was not provided at the visit, it will be sent with a letter requesting the return of the study medication. If we do not receive the remaining study medication, the study team will create a note to file documenting that the participant completed the study, but any remaining study medication was not returned.

If we are having trouble contacting the participant to schedule their visit within the window, we will send a follow-up letter asking them to call us by a certain date if they wish to continue participating. If we do not hear from the participant by the end of the day on the date specified in the letter, we will assume they are no longer interested and withdraw them from the study. The letter will include a request that the participant return any remaining study medication in the enclosed postage-paid envelope. The study team will properly dispose of any remaining medication after completing a final pill count. If we do not receive the remaining study medication,

the study team will create a note to file documenting that the participant was withdrawn from the study, but any remaining study medication was not returned.

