At every visit (depending on previous lab results), participants will have interim drug safety assessments (AST, ALT, urine pregnancy as indicated) and an assessment of medical/medication changes and potential drug or procedural side effects. Participants with baseline or month 1 AST or ALT between 1.5 upper limit of normal (ULN) and ≤2 x ULN at the preceding visit will have repeat AST and ALT values drawn at 3-, 6-, 12- and 15-month visits as well. The proposed study drug monitoring plan exceeds that required by the FDA for IPE (Vascepa) which states that patients with hepatic impairment should have ALT and AST levels monitored periodically during therapy.

All research visits will occur at the William S. Middleton Memorial Veterans Hospital in Madison, Wisconsin with the exception of visits that can occur remotely over the phone (3-, 6-, 12- and 15-). These remote phone visits will depend on AST and ALT values as noted above and if they need a urine pregnancy test. If baseline or month 1 AST or ALT do not fall between 1.5 upper limit of normal (ULN) and  $\leq$ 2 xULN and they are not of childbearing potential, these visits can occur by phone. In this case, the phone visit will be scheduled at the preceding in-person visit, or by a coordinator 1 – 3 weeks prior to phone visit date. The study team will attempt contact with the participant 5 times, at different times of the day/evening over a 2-week period, as well as leave at least two voicemails. If contact for phone visit is still unsuccessful at this point, the visit will be marked as incomplete.

All neuroimaging will occur in the UW Wisconsin Institutes for Medical Research (WIMR) (a 10-minute walk from the physically-adjacent Madison VA Hospital). All MR images will be reviewed before participants begin treatment to ensure high quality data were obtained.

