#### **Analysis Population**

All analyses will be performed on an intent-to-treat basis as far as follow-up allows. All randomized patients will be encouraged to continue to be assessed and, if they consent, included in the analysis regardless of compliance with study medication. Follow-up rates in similar studies conducted by the PI are between 94-97% (see **Preliminary Studies**). We therefore conservatively predict 90% follow-up in this 18-month trial. For patients missing final values (month 18) but having intermediate measurements of outcomes (month 9), final outcomes will be imputed using expectations from longitudinal data analyses conditional on available data, with random noise added using standard errors taken from the residuals of these analyses. Patients missing all post-baseline values will be omitted. Sensitivity analyses will be conducted to quantify potential biasing effects of dropout on estimated treatment effects and multiple imputation used to quantify the additional variation. There will be no formal interim analyses for efficacy as this is a proof-of-concept study and the rCBF and CSF biomarker changes do not have any clearly known clinical consequences at this time.

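### Silence after one dated letter is treated as withdrawal from the whole study, with no provision to seek the month-9 or month-18 outcomes; this should be reconciled with the phone-visit and follow-up rules.

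*Combined protocol and SAP*

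**What the plan says.** Three places in the combined protocol and SAP deal with a randomised participant who cannot be reached or does not attend.

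- **Trial Design Summary.** The trigger is "If we are having trouble contacting the participant to schedule their visit within the window". A letter with a reply-by date follows. "If we do not hear from the participant by the end of the day on the date specified in the letter", then "we will assume they are no longer interested and withdraw them from the study". The letter also asks for return of remaining study medication. No visit type, number of earlier attempts or length of reply period is given. The same section accepts late visits: "it is possible that the actual visit will be outside of this window".
- **Study Protocol (Table 2).** For visits held by phone (months 3, 6, 12 and 15) the team will "attempt contact with the participant 5 times, at different times of the day/evening over a 2-week period" and leave at least two voicemails. "If contact for phone visit is still unsuccessful at this point, the visit will be marked as incomplete". Neither a letter nor withdrawal is mentioned. The section also encourages an early termination visit, with Visit 8 procedures, for those who discontinue.
- **Analysis Population.** "All randomized patients will be encouraged to continue to be assessed", and those who consent are analysed whatever their compliance with study drug. Intent-to-treat applies to the extent that follow-up permits. Month 18 is imputed where month 9 exists. "Patients missing all post-baseline values will be omitted".

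**The concern.** The letter rule turns silence into withdrawal from the study, and not merely from study drug. Once it is applied, nothing in the text tells staff to try again for the month-9 or month-18 MRI, which supplies the primary endpoint. The participant has not refused anything; the protocol ends follow-up on their behalf.

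People who stop answering may differ from those who reply, for example in health, in how they tolerate the capsules or in their circumstances. The documents give no data on this, so the missingness is possibly, not demonstrably, informative. What is at stake is whether some primary outcomes are lost that one more contact might have secured, and whether staff at the same site would handle the same failed contact in two different ways.

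**Working it through.** **1. The rules side by side**

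| Place | Trigger | Stated effort | Consequence | Later outcomes sought? |
|---|---|---|---|---|
| Trial Design Summary | Trouble reaching the participant to schedule a visit; any visit type | Not stated, then one dated letter | Withdrawn from the study | Not provided for |
| Study Protocol (Table 2) | Phone visit not reached (months 3, 6, 12, 15) | 5 attempts over 2 weeks, at least two voicemails | Visit marked incomplete | Participant remains in the study |
| Analysis Population | Any randomised patient | Encouragement to continue | Assessed and, with consent, analysed | Yes |

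The first two rows do not refer to each other. A phone visit also has to be scheduled, so the wording of the first row can reach the situation in the second.

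Elsewhere the plan separates stopping drug from leaving the study. Inclusion/Exclusion Criteria lets people who start an anticoagulant stop study drug and stay for observation. The COVID-19 section kept participants who missed their final visit until they could attend. The letter rule makes no such separation.

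**2. What happens to the primary outcome**

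Table 2 schedules MRI at months 0, 9 and 18 only.

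- Presumed withdrawn before month 9, no early termination MRI: there is no post-baseline rCBF value, so Analysis Population omits the participant.
- Presumed withdrawn after a month-9 MRI: month 18 is imputed, so the participant stays in the analysis with a modelled value.
- Presumed withdrawn over the final visit itself: no later scheduled visit remains, but a late visit, which the plan otherwise accepts, is no longer sought.

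**3. The plan's own sample size**

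Inputs from Power Calculations: effect size d = 0.57, two-sided alpha 0.05, 67 per arm, 10% drop-out, 150 randomised.

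For a two-sample t-test with n per arm, the noncentrality is d × √(n/2), on 2n − 2 degrees of freedom.

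- n = 67: 0.57 × √33.5 = 3.30 on 132 degrees of freedom; power 90.6%.
- Required n for 90% power: 65.66, so 66 per arm against the 67 stated.
- Drop-out: 134 / 0.90 = 148.9, so 149 against the 150 stated; 150 × 0.90 = 135.

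The stated figures reproduce.

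**4. Sensitivity to the number lost**

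The documents give no count of letter-rule withdrawals, so the range below is assumed. Losses are treated as contributing nothing, which is pessimistic for anyone with a month-9 scan.

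| Month-18 values out of 150 | Losses | t-test power at d = 0.57 |
|---|---|---|
| 140 | 10 (5 of the 15 budgeted recovered) | 91.8% |
| 135 | 15 (as planned) | 90.8% |
| 125 | 25 (10 beyond plan) | 88.5% |
| 120 | 30 (15 beyond plan) | 87.2% |

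Recovering 5 people adds about 1 percentage point. Doubling the planned loss costs 90.8 − 87.2 = 3.6 points.

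**The case against.** The strongest reply is that the letter rule is narrower than it looks. It comes into play only after contact has already proved difficult, and the letter asks whether the person wishes to continue. For phone visits the plan has its own, milder rule, and a specific rule ordinarily governs over a general one. The letter rule also follows directly on text about a delayed final visit and returned medication, so it may have been written mainly with in-person visits in mind. Lateness alone does not trigger it. Month 18 is imputed when month 9 exists, dropout sensitivity analyses with multiple imputation are planned, and an early termination visit is encouraged. A 10% loss is budgeted, and retention of 94–97% is reported from earlier studies.

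Much of this stands, and it rules out three stronger readings.

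- A reader might infer that one missed interim contact forfeits the month-18 outcome. The documents do not support that: withdrawal needs contact trouble plus an unanswered letter, and an unreached phone visit is only marked incomplete.
- A reader might infer a breach of intent-to-treat. The commitment is qualified by available follow-up and by consent, and its wording on compliance concerns study drug and not loss of contact. The two rules are poorly aligned, but neither strictly violates the other.
- A reader might infer a material loss of power. The table above does not show one.

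What the reply does not remove is the rule itself. Months 1, 9 and 18 are in person, so the milder phone rule does not cover them. An early termination visit is hard to obtain from someone who cannot be reached. Imputation replaces an observed outcome with a modelled one, and it is available only after month 9. Finally, silence is not a refusal of consent.

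**Conclusion.** The point holds as an inconsistency that creates avoidable missing primary data. The letter rule presumes withdrawal from the whole study and provides for no attempt at the month-9 or month-18 outcomes, while the phone-visit rule and the follow-up aim point the other way.

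The number affected is unknown, and no difference between arms or direction of bias can be shown from the documents. The power effect is small: about 1 point gained under the assumed recovery of 5 people, and 87.2% even if total losses doubled to 30. Those figures rest on the plan's effect size of 0.57 and on a simple two-sample t-test without the baseline covariate. The case for change therefore rests on completeness of the primary outcome and consistent handling, together with the low cost. It is a worthwhile correction and not a flaw that undermines the design.

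**What to change.** In Trial Design Summary, amend the letter rule so that:

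1. non-response is recorded as loss of contact, with the affected visits marked as missed, in line with the phone-visit rule;
2. the status of withdrawn is reserved for participants who expressly withdraw consent;
3. a further contact attempt is made for the month-9 and month-18 outcome visits unless the participant has declined.

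Add a cross-reference between this rule, the phone-visit rule and Analysis Population, so that a given failed contact has one consequence.

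The provisions for returning study medication can stay as they are. Because presumed withdrawal currently settles the matter by default, the sponsor should state how study-drug dispensing is handled while a participant is out of contact; this review does not propose a rule.

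The cost is a short wording change, that statement on dispensing, and a few extra calls or letters. The downside is further contact with people who have not replied, and some of them will still not respond.

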#### Recruitment

Potential subjects will be recruited from the William S. Middleton Memorial Veterans Hospital (Madison VA), surrounding VA Community-based Outpatient Clinics (CBOCs) (Baraboo, Beaver Dam, Janesville, WI and Rockford and Freeport, IL) through VA primary care and specialty care clinics, physician referrals, electronic message boards in VA waiting rooms, letters, brochures, emails, newsletters, newspaper and web-based advertisements, educational and outreach events, including our Madison VA's Annual Research Day, and from the ADRC Clinical Core or other ADRC-affiliated studies through similar methods. Our partners and affiliates may use their websites, newsletters, and emails to announce open enrollment into our study or educational and outreach events being led by us. Veterans' records will be flagged in the VA's VistA and Computerized Patient Record System to obtain release of information from participants to 1) review their medical records for eligibility in the study and 2) safety measures to place a note in Veterans' records to indicate the Veteran is in our study and to clarify the participant is on medication that could be a contraindication for medical procedures or other health care procedures the patient may have to undergo. Additionally, clinic providers will provide descriptive study materials to potential enrollees.

The first steps for screening potential participants will be to 1) provide an explanation of the goals, scope and nature of the study, 2) complete a Screening Checklist, 3) obtain permission for study personnel to keep their contact information and Screening Checklist for the duration of the screening process, and 4) to exclude individuals who fall into the exclusion criterion. If the potential participant does not desire or is ineligible to be part of this study, any information collected during the screening interview, including contact information will be retained in order to avoid re-contact in the future. During the telephone screening process, participants will be asked a series of questions to screen out people who do not meet the inclusion criteria (age (50-75 years), and Veteran status criteria). We will also ask if they have a parental history of AD to include in final analyses. In addition, we will exclude participants who meet any of our exclusion criteria which include being allergic to fish and/or shellfish, currently using anticoagulants or are taking medications that adversely interfere with IPE, are not MRI compatible, pregnant, etc. The reason for this telephone screening is to prevent the inconvenience to potential subjects of attending a screening visit who are unable to participate in the study because they are not eligible for MRI. LP, or randomization to IPE study medication. If no exclusions arise and the patient indicates desire to participate in the study, they will be scheduled for a screening visit. Some potential participants may have the screening occur in person, if they are at the Madison VA Hospital as part of their normal health care routine and express interest in participating in the study. In general, the study team will resort to phone screening participants. The study team will attempt to reach the participant at varying times of the day up to three times then will leave a voicemail message for the participant, stating that "This is [research team member's name] from the Madison VA leaving a message for [participant name] regarding their interest in our VA Research Study. I would be happy to discuss this study in more detail with you. I may be reached at [phone number]. I look forward to talking to you soon and answering what questions you may have." If someone other than the participant answers the phone, our team will make the same comment and emphasize that we cannot disclose the type of study without permission of the potential participant. Contact information will be left with the household member for the potential participant to call our team. If no response from the potential participant is received after leaving a message with another family member, another attempt will be made just in case the participant's family member forgot to relay the message. If no response is received following that contact, a followup letter with contact information will be mailed as a final contact initiation. After that, it will be assumed the potential participant is no longer interested in the study. In accordance with VA rules,

the participant's contact information will be kept in a file in a locked drawer, in a locked office, of a restricted-access section (the VA GRECC) of the VA.

Wisconsin has 436,630 total living Veterans (93% non-Hispanic white, 3.6% African American, 1.3% Hispanic or Latino, 8.6% women) and there are 191,500 Wisconsin Veterans between the study eligibility ages of 50-75 years (44% of total Wisconsin Veterans). The Madison VA Hospital serves 130,000 Veterans living in 15 counties in south-central Wisconsin and in five counties in northwestern Illinois. Assuming that approximately 44% of these Veterans are in the 50-75 year age range (57,200) and that approximately 13% will have a parent with AD (based on AD prevalence estimates for Wisconsin), we estimate that we will have a recruitment pool of approximately 7500 Veterans between the ages of 50-75 years with a parent with AD. Based on the gender and race/ethnicity of Veterans in Wisconsin, we assume that approximately 580 (7.8%) will be women, 270 (3.6%) African American, and 98 (1.3%) Hispanic/Latino.

As our ADRC is jointly sponsored by the University of Wisconsin and our VA, many of our ADRC-related outreach events include Veterans and occur within our VA hospital. While the pool of participants from whom we draw for the proposed VA study is somewhat different than our ADRC participant pool, our ADRC team has a strong track record of outreach and recruitment and has established networks and infrastructure on which to build for the proposed VA-based study. As of September 1, 2014, the Wisconsin ADRC had enrolled 251 cognitively-healthy participants with parental history of AD who fall within the proposed age range (50-75 years). Each month, the ADRC recruits on average 10 new participants and has a high number of cognitively-healthy middle-aged and older adults interested in study participation. Thus, we anticipate a high level of interest in this age group for the proposed study as well. In addition, the PI and her colleagues have successfully recruited participants from the community prior to the funding of the Wisconsin ADRC in 2009. As Leader of the ADRC Clinical Core, [name] is integrally involved in the recruitment and retention of participants, including persons from communities of color. The Wisconsin ADRC has a Minority Recruitment Satellite Program which works closely with African American communities in south central Wisconsin and northern Illinois. While Wisconsin is approximately 6.5% African American, 11% of Wisconsin ADRC participants are African American. Adult children of persons with AD are very motivated to participate in research and have had a very high retention rate (94-97%) in our prior trials. Thus, a recruitment rate of 4-5 new participants per month for the proposed trial is very feasible and should allow us to successfully complete recruitment over a 38-month period. Retention efforts will include postvisit feedback forms, interim safety telephone calls, and birthday and thank-you cards, newsletters from our VA GRECC and ADRC, and invitations to our ADRC's Annual November Lecture on Alzheimer's disease.

